3.3. Exploratory Objectives

The exploratory objectives of the study are:

4. INVESTIGATIONAL PLAN

[figure not shown]
4.1. Overall Study Design and Plan

This is a Phase 4, single-arm, multicenter, open-label study to evaluate the impact of apremilast (CC-10004), either in monotherapy or with stable methotrexate (MTX) on MRI outcomes in subjects with active PsA with up to 5 years of disease duration (since diagnosis).

Approximately 120 subjects will receive apremilast 30 mg BID, after a 5-day titration period, with or without stable MTX. All subjects will be permitted to take nonsteroidal anti-inflammatory drugs (NSAIDs) and/or low-dose oral glucocorticoids (prednisone \leq 10 mg/day or equivalent) throughout the study. The NSAIDs and low-dose oral glucocorticoids must be on a stable regimen for at least 4 weeks prior to baseline. MTX (\leq 25 mg/week) will be permitted if duration of treatment is \geq 6 months and on a stable regimen for at least 3 months prior to baseline. In addition, the stable doses of MTX, NSAIDs, and low-dose glucocorticoids must be continued from Day 1 through the Week 24 Visit. Change in doses, increase or decrease, and/or discontinuation will not be allowed except for safety reasons or for lack of availability. After the Week 24 Visit, the doses of MTX, NSAIDs, or glucocorticoids may be adjusted as clinically required.

This is a 56-week study comprised of 3 phases:

[figure not shown]
- Screening Phase – up to 4 weeks
- Single-arm, Open-label Treatment Phase – Weeks 0 to 48
 - 120 subjects will receive apremilast 30 mg BID (after a 5-day titration period) for the entire duration of this phase.

- Observational Follow-up Phase – 4 Weeks
 - All subjects who complete the study or discontinue early will participate in the 4-week Post-Treatment Observational Follow-up Phase.

The study schematic is presented in [Figure 1](#).

Figure 1: Overall Study Design

BID = twice daily; MTX = methotrexate; Wk = Week.

4.2. Study Endpoints

Efficacy and safety endpoints are listed in Sections 4.2.1 through 4.2.2, respectively. Derivations of select efficacy and safety endpoints are described in Sections 4.2.4 and 4.2.5, respectively.

4.2.1. Efficacy Endpoints

The following sections provide the efficacy endpoints as specified in the protocol.

4.2.1.1. Primary Efficacy Endpoint

The primary endpoint of the study is the change from baseline in the composite score of bone marrow edema (BME), synovitis, and tenosynovitis assessed by Psoriatic Arthritis Magnetic Resonance Imaging Score (PsAMRIS) at Week 24.

[figure not shown]
4.2.1.2. Secondary Efficacy Endpoints

[figure not shown]
- Change from baseline in the composite score of BME, synovitis, and tenosynovitis assessed by PsAMRIS at Week 48.
- Change from baseline in the composite score of BME and synovitis assessed by PsAMRIS at Weeks 24 and 48.
- Change from baseline in the PsAMRIS total inflammation score (BME, synovitis, tenosynovitis and periarticular inflammation) at Weeks 24 and 48.
- Change from baseline in BME assessed by PsAMRIS at Weeks 24 and 48.
- Change from baseline in synovitis assessed by PsAMRIS at Weeks 24 and 48.
- Change from baseline in tenosynovitis assessed by PsAMRIS at Weeks 24 and 48.
- Change from baseline in periarticular inflammation assessed by PsAMRIS at Weeks 24 and 48.

- Change from baseline in the PsAMRIS total damage score (erosion + bone proliferation) at Weeks 24 and 48.
- Change from baseline in bone erosion assessed by PsAMRIS at Weeks 24 and 48.
- Change from baseline in bone proliferation/enthesophytes assessed by PsAMRIS at Weeks 24 and 48.
- Change from baseline in the Swollen Joint Count (SJC) at Weeks 24 and 48.
- Change from baseline in the Tender Joint Count (TJC) at Weeks 24 and 48.
- Change from baseline in the Clinical Disease Activity Index for Psoriatic Arthritis (c-DAPSA) Score at Weeks 24 and 48.
- Change from baseline in Spondyloarthritis Research Consortium of Canada (SPARCC), in subjects with preexisting enthesopathy at Weeks 24 and 48.
- Change from baseline in the Leeds Enthesitis Index (LEI), in subjects with preexisting enthesopathy at Weeks 24 and 48.
- Proportion of subjects with baseline enthesitis whose enthesitis improves to 0 at Weeks 24 and 48.
- Change from baseline in the Leeds Dactylitis Index (LDI), in subjects with preexisting dactylitis at Weeks 24 and 48.
- Proportion of subjects with baseline dactylitis whose tender dactylitis count improves to 0 at Week 24 and 48.
- Change from baseline in the Psoriatic Arthritis Disease Activity Score (PASDAS) at Weeks 24 and 48.
- Change from baseline in the evaluator's global assessment of disease activity at Weeks 24 and 48.
- Change from baseline in the subject's global assessment of disease activity at Weeks 24 and 48.
- Change from baseline in the subject's assessment of pain at Weeks 24 and 48.
- Change from baseline in Health Assessment Questionnaire-Disability Index (HAQ-DI score) at Weeks 24 and 48.
- Change from baseline in the peripheral enthesitis inflammation index assessed by WB-MRI at Weeks 24 and 48.
- Change from baseline in peripheral joints inflammation index assessed by WB-MRI at Weeks 24 and 48.
- Change from baseline in the total peripheral (joints and enthesitis) inflammation index assessed by WB-MRI at Weeks 24 and 48.

- Change from baseline in the Bath Ankylosing Spondylitis Disease Activity Index BASDAI (for subjects deemed to have PsA spondylitis by the investigator and with BASDAI item 2 \geq 4 at baseline) at Weeks 24 and 48.
- Change from baseline in the PsAID-12 at Weeks 24 and 48.

4.2.1.3. Exploratory Efficacy Endpoints

4.2.2. Safety Endpoints

The following safety parameters will be evaluated throughout the duration of the study:

- Adverse events (AEs)
 - Type, frequency, severity and relationship of adverse events to study medication
 - Number of subjects who discontinue study medication due to any adverse event
- Deaths
- Laboratory evaluations
 - Laboratory marked abnormalities (refer to Appendix [A1.2](#))
 - Observed value and change from baseline over time in continuous laboratory parameters
 - Shifts from baseline to post-baseline time points and to the worst post-baseline value in terms of low/normal/high/both low and high in laboratory parameters, as appropriate
- Vital signs and weight

- Observed value and change from baseline over time in vital signs (weight, temperature, pulse, and blood pressure)
- Shifts from baseline to post-baseline time points, and to the worst post-baseline value in terms of normal/abnormal in pulse and blood pressure (normal ranges are defined as: 60-100 beats/minute for pulse, 90-140 mmHg for systolic blood pressure, 35.5-37.9 C for temperature, and 60-90 mmHg for diastolic blood pressure)
- Observed value, change and percent change from baseline over time in weight

4.2.3. Health-related Quality of Life Endpoints

All endpoints related to the health-related quality of life (shown below) are included in the efficacy endpoints above.

Table 1: Health-related Quality of Life Endpoints

Secondary	The European League Against Rheumatism Psoriatic Arthritis Impact of Disease 12 domains (PsAID-12)	Change from baseline in the PsAID-12	Week 24 Week 48
Exploratory			

4.2.4. Derivations of Efficacy Endpoints

The definition of baseline, applicable to all continuous efficacy endpoints, is given in Section 5.4. Change from baseline is calculated as on-treatment value minus the baseline value. Handling of time points is described in Section 5.5.

4.2.4.1. Magnetic Resonance Imaging (MRI)

In this study, the [REDACTED]

The MRI assessments will be conducted following the procedures outlined in the MRI manual, and must be performed on the same day of or within 7 days after the clinical visit. Therefore, the baseline MRI could be performed 7 days after the first administration of IP. The subsequent MRIs should be performed at Week 24 + 7 days and Week 48 + 7 days. All MRI visits should be scheduled well in advance to allow for proper planning. In addition, it is recommended to schedule 2 MRI visits (an initial and a repeat visit) for each MRI time point to ensure a high-quality MRI scan at each protocol-specified time point. The initial and repeat MRI visits should be scheduled approximately 7 to 14 days apart. If the initial MRI scans are of acceptable quality, then the scheduled repeat MRI session can be canceled. Maximum two repeated MRI scans can be scheduled. All images will be read regardless of deviations in acquisition window.

4.2.4.2. MRI of the Most Affected Hand

The conventional MRI assessment will be performed at baseline, Week 24, Week 48 and ET visit on the hand with the greater inflammatory burden of swollen joints and/or dactylitis. If both hands are equally affected, the dominant hand will be designated as the index hand.

4.2.4.3. PsAMRIS

The Outcome Measures in Rheumatology Clinical Trial (OMERACT) Psoriatic Arthritis Magnetic Resonance Imaging Score (PsAMRIS) is a validated scoring system used to assess the images from the MRI of the most affected hand.

OMERACT PsAMRIS assesses metacarpophalangeal (MCP), proximal interphalangeal (PIP), and distal interphalangeal (DIP) joints of fingers 2 to 5, and evaluates synovitis (score 0-3), flexor tenosynovitis (score 0-3), periarticular inflammation (absent or present), bone edema (score 0-3), bone erosion (score 0-10) and bone proliferation/enthesophytes (absent or present).

All MRI readings are performed by two radiologists blinded to visit sequence and the patients. The adjudication of the results, when two readers are involved, will be done through the consensus procedure between the two readers. The readers will be able to share the screen and discuss the data, then amend the final scoring. The adjudication might involve the original reading and repeat reading. The adjudication score is considered as final assessment score and used for analysis. The intent of adjudication is to verify those cases that will have the greatest impact on results.

For more detailed information on the specific procedures and the consistent acquisition of MRI images, please refer to the Imaging Charter. The handling of missing data in PsAMRIS will be discussed in Section [4.2.4.4](#).

4.2.4.3.1. Synovitis

Synovitis is to be scored 0-3 at MCP, PIP and DIP joints of fingers 2 to 5. Grading scale: score 0 is normal, while score 1-3 is mild, moderate, severe, respectively. A total of 12 joints in the most affected hand are evaluated, the maximum possible score is 36.

4.2.4.3.2. Flexor Tenosynovitis

Flexor tenosynovitis is to be scored 0-3 at the same 12 joint regions as evaluated for synovitis. The maximal thickness of enhancing/bright signal tenosynovium is to be assessed as follows: 0: none; 1: < 1/2 tendon thickness; 2: ≥ 1/2 and < 1 tendon thickness; 3: ≥ 1 tendon thickness. Like the synovitis score in Section 4.2.4.3.1, the maximum possible score is 36.

4.2.4.3.3. Periarticular Inflammation

Periarticular inflammation is to be scored 0–1 separately at volar and dorsal aspects of the same 12 joint regions as evaluated for synovitis and flexor tenosynovitis. Grading scale: 0: absent; 1: present. Thus, the maximum possible score is 24.

4.2.4.3.4. BME score assessed by PsAMRIS

Bone marrow edema score, the bone edema score from PsAMRIS, is assessed on a scale of 0-3, based on the proportion of bone with edema, compare to the “assessed bone volume”, judged on all available images; where 0: no edema; 1: 1–33% of bone oedema; 2: 34–66% of bone oedema; 3: 67–100% of bone oedema (as per RAMRIS¹). A total of 12 joint regions are evaluated, and as each joint has proximal and distal components, thus the maximum possible score is 72.

4.2.4.3.5. Bone Erosion

Bone erosion is assessed on a scale of 0-10, based on the proportion of eroded bone compared to the “assessed bone volume,” judged on all available images: 0: no erosion; 1: 1–10% of bone eroded; 2: 11–20%, etc. The “assessed bone volume” is from the articular surface (or its best estimated position if absent) to a depth of 1 cm (as per RAMRIS¹). A total of 12 joints in the most affected hand are evaluated and each joint has proximal and distal components; the maximum possible score is 240.

4.2.4.3.6. Bone Proliferation

Bone proliferation is to be scored 0–1 at MCP, PIP, and DIP joints of fingers 2 to 5. Grading scale: 0: absent; 1: present. Thus, the maximum possible score is 12.

4.2.4.3.7. Inflammation Score of BME, Synovitis and Tenosynovitis

To give each of the three symptoms equal weighting, the inflammation score of BME, synovitis and tenosynovitis is the [REDACTED]. The maximum possible score is 216.

4.2.4.3.8. Composite Score of BME and Synovitis

The composite score of BME and synovitis is the [REDACTED] like the inflammation score estimation in Section 4.2.4.3.7. The maximum possible score is 144.

4.2.4.3.9. Total Inflammation Score

The total inflammation score consists of BME, synovitis, tenosynovitis and periarticular inflammation. The total inflammation score is computed as [REDACTED]

[REDACTED]. The maximum possible score is 288.

4.2.4.3.10. Total Damage Score

The total damage score consists of erosion score and bone proliferation score. To give these 2 symptoms equal weights, the total damage score is [REDACTED]. The maximum possible score is 480.

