**Table 12: Study Endpoints**

Endpoint	Name	Description	Time Frame
Primary	Psoriatic Arthritis Magnetic Resonance Imaging Score (PsAMRIS) Inflammation Score of bone marrow edema [BME] + synovitis + tenosynovitis	Change from baseline in the composite score of BME, synovitis, and tenosynovitis assessed by PsAMRIS	Week 24
Secondary	Efficacy		
	PsAMRIS Inflammation Score of BME + Synovitis + Tenosynovitis	Change from baseline in the composite score of BME, synovitis, and tenosynovitis assessed by PsAMRIS	Week 48
	PsAMRIS BME + Synovitis	Change from baseline in the composite score of BME and synovitis assessed by PsAMRIS	Week 24 Week 48
	PsAMRIS Total Inflammation Score (BME + Synovitis + Tenosynovitis + Periarticular Inflammation)	Change from baseline in the PsAMRIS total inflammation score	Week 24 Week 48
	PsAMRIS BME	Change from baseline in BME assessed by PsAMRIS	Week 24 Week 48
	PsAMRIS Synovitis	Change from baseline in synovitis assessed by PsAMRIS	Week 24 Week 48
	PsAMRIS Tenosynovitis	Change from baseline in tenosynovitis assessed by PsAMRIS	Week 24 Week 48
	PsAMRIS Periarticular Inflammation	Change from baseline in periarticular inflammation assessed by PsAMRIS	Week 24 Week 48
	PsAMRIS Total Damage Score (erosion + bone proliferation)	Change from baseline in the PsAMRIS total damage score (erosion + bone proliferation)	Week 24 Week 48
	PsAMRIS Erosion	Change from baseline in bone erosion assessed by PsAMRIS	Week 24 Week 48
	PsAMRIS Bone Proliferation	Change from baseline in bone proliferation/enthesophytes assessed by PsAMRIS	Week 24 Week 48
	Swollen Joint Count (SJC)	Change from baseline in the SJC	Week 24 Week 48
	Tender Joint Count (TJC)	Change from baseline in the TJC	Week 24 Week 48

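### Does the implied factor of 20 on bone proliferation in the PsAMRIS total damage score call for a plain-sum version beside it?

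*SAP*

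**What the plan says.** **Components.** SAP 4.2.4.3.5 scores erosion 0–10 at the proximal and distal bone of 12 joints: "the maximum possible score is 240". SAP 4.2.4.3.6 scores bone proliferation as absent or present at the same 12 joints: "Thus, the maximum possible score is 12".

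**Total damage score.** SAP 4.2.4.3.10 states the aim, "To give these 2 symptoms equal weights, the total damage score is", and the result, "The maximum possible score is 480". The formula between them is blacked out, which is not a fault of the plan.

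**Sibling scores.** SAP 4.2.4.3.7 uses the same device for the primary composite ("To give each of the three symptoms equal weighting, the inflammation score of BME, synovitis and tenosynovitis is the", with a stated maximum of 216). SAP 4.2.4.3.8 ("The maximum possible score is 144") and 4.2.4.3.9 ("The maximum possible score is 288") follow it.

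**Labels.** Protocol Table 12 names the endpoint "PsAMRIS Total Damage Score (erosion + bone proliferation" (the closing bracket follows in the table). The lists in SAP 4.2.1.2 and 9.2 are worded in the same way. None shows a factor. The scoring sheet in Protocol Appendix P grades the components and gives no rule for totals.

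**Separate reporting.** Protocol Table 12 and SAP 4.2.1.2 also list erosion and bone proliferation as secondary endpoints in their own right at Weeks 24 and 48. Protocol 9.6.2 promises descriptive summaries and 95% confidence intervals for every secondary endpoint.

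**The concern.** A reader who sees only the plus sign may take total damage to be a plain sum from 0 to 252, when the stated maximum implies a score from 0 to 480 in which each yes/no proliferation reading is worth 20 points. That is the full erosion range of a joint: two bone sites going from 0 to 10. The sibling composites imply factors of only 2 and 3.

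Total damage is the composite for the first-listed secondary objective, structural progression. If erosion changes little, a handful of proliferation readings, right or wrong, could set the mean change and its spread. The result could then be reported as structural progression in general. The visible text offers no second weighting to test this; the sensitivity analyses in SAP 6.1 vary only the population.

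**Working it through.** **1. Reproduce the stated maxima.** There are 12 joints.

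- Erosion: 12 × 2 × 10 = 240. Proliferation: 12 × 1 = 12.
- Let a and b be the weights. Equal weights means 240a = 12b; the stated maximum means 240a + 12b = 480. The only solution is a = 1, b = 20. The plain sum is 240 + 12 = 252.
- The same rule applied to bone marrow edema (72), synovitis (36), tenosynovitis (36) and periarticular inflammation (24) gives 72 + 2×36 + 2×36 = 216; 72 + 2×36 = 144; and 216 + 3×24 = 288. All match the SAP.

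So the factor of 20 is firm, and it is the SAP's general convention and not an oddity of one section.

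**2. Leverage of one joint.** Planned evaluable subjects: 120 × 0.8 = 96 (check: 1.96 × 6.2/√96 = 1.24, the stated half-width). Joints: 96 × 12 = 1,152.

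| | Equal-weight score | Plain sum |
|---|---|---|
| One joint, share of range | 20/480 = 4.2% | 1/252 = 0.4% |
| One net changed joint, shift in mean | 20/96 = 0.21 | 1/96 = 0.01 |
| The same shift, share of range | 0.04% | 0.004% |
| Five joints (5/1,152 = 0.43%), shift in mean | 100/96 = 1.04 | 5/96 = 0.05 |

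The shifts in points are on different scales. Relative to range, the ratio is (20/480)/(1/252) = 10.5, not 20.

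**3. Would proliferation dominate?** Let s be the SD of the erosion change and p the chance that a joint's proliferation reading changes by ±1, with no net drift, independent joints, and no correlation with erosion. The proliferation count then has change variance 12p, and its share of the total variance is

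- equal-weight score: 400 × 12p/(400 × 12p + s²) = 4800p/(4800p + s²)
- plain sum: 12p/(12p + s²)

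The documents give neither s nor p. The ranges assumed are s from 1 to 6.2 (6.2 is borrowed from the inflammation composite) and p from 0.1% to 5%.

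| s | p | Equal-weight score | Plain sum |
|---|---|---|---|
| 6.2 | 0.1% | 4.8/43.24 = 11% | 0.03% |
| 4 | 0.1% | 4.8/20.8 = 23% | 0.07% |
| 2 | 2% | 96/100 = 96% | 5.7% |
| 1 | 5% | 240/241 = 99.6% | 0.6/1.6 = 37.5% |

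The two shares are equal in the weighted score when s = 20√(12p): 2.2 at p = 0.1%, 6.9 at 1%, 15.5 at 5%. The answer depends wholly on the assumed inputs.

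**4. What would a plain sum add?** From the last column, erosion carries 62.5% to over 99% of its variance, so it largely repeats the erosion endpoint. Most of it can also be worked out from results already planned. Write E, P and W = E + 20P for the changes in erosion, proliferation and the prespecified total. If the same subjects contribute to all three:

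- mean of plain sum = mean E + mean P
- proliferation's part of the prespecified mean = 20 × mean P
- Var(W) = Var(E) + 400 Var(P) + 40 Cov(E,P), so Var(E + P) = 0.95 Var(E) − 19 Var(P) + 0.05 Var(W)

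Check at s = 2, p = 2%: 0.95×4 − 19×0.24 + 0.05×100 = 3.80 − 4.56 + 5.00 = 4.24 = 4 + 0.24. So the SD and the simple normal-theory interval follow from three reported SDs, up to rounding. Only the proportion beyond the smallest detectable change does not.

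**The case for a change.** The best case for a change is that it costs one derivation and one table. It would also settle the alternative before results are seen, so that nobody picks a weighting afterwards. Protocol 1.3.3 says that longer follow-up is needed to detect change in erosions on MRI, which makes small erosion changes at Week 24 plausible; that is when a heavily weighted binary item matters most. The labels are silent on the weighting, and the proportion of subjects beyond the smallest detectable change cannot be rebuilt for a plain sum.

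Some of this stands. The factor of 20 is real, the lists do not show it, and a single reading does carry more of the range here than elsewhere (4.2%, against 3/288 = 1.0% for a periarticular reading). The underlying property is not peculiar to this score, though: equalising maxima gives each component the same range per joint, 6 points in the inflammation scores and 20 here.

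The rest does not carry a change. SAP 4.2 sends the reader to 4.2.4 for derivations, where the weighting is stated, and a plus sign names components in Table 12 for the equally weighted inflammation scores too. The absence of a plain sum can be asserted only for the visible text, because the exploratory sections and the derivation of the smallest detectable change are not shown. A rule that conclusions hold only where two versions agree would need a definition of agreement, and it would sit badly in a single-arm study that analyses its secondary endpoints descriptively.

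**Conclusion.** No change to the plan follows. The SAP prespecifies equal weighting, states the resulting maximum, and applies one convention across all four composites; nothing in either document calls for a plain sum. The implied factor of 20 rests on the stated maxima together with the equal-weights sentence, and is secure on that basis. That proliferation would dominate the change is not shown: a share of 11% to over 99% of the variance, from SDs and change rates that the documents do not give, covers everything from minor to total.

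If it did dominate, the separate erosion and proliferation results at the same visits would show it, since proliferation's part of the mean is 20 times a reported figure. The companion score would mostly restate erosion, and the one item it would add is a proportion based on a derivation that is not shown. The primary endpoint, the two component endpoints and the sample size of 120 are unaffected. Writing the weighting and the 0–480 range into table titles would help readers, but that is presentation that analysts can supply and it alters no result.

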4.2.4.3.11. Smallest Detectable Change (SDC)

[figure not shown]
To maintain objectivity in the evaluation of imaging, two different readers will evaluate all time points for a given subject. All time points for a subject will be presented in arbitrary order. The reviewers will have no knowledge of the time point chronological sequence, subject identity.

[figure not shown]

[figure not shown]
4.2.4.4. Handling of Missing Data in PsAMRIS

4.2.4.4.1. Handling of Missing Individual Joint Evaluation in PsAMRIS

PsAMRIS readings between the two readers will be adjudicated by the consensus method. For more detailed information on the adjudication of MRI images, please refer to the Imaging Charter. Missing or unclassifiable readings for individual joint/location evaluations will be imputed by the following guideline:

[figure not shown]

